Map DSS tool, if different from the already selected targets by the radiologist per standard of care. Ultimately, the clinical radiologist will make the final decision on the targets to be biopsied. MR-targeted biopsies will be done by using a Uronav MR-US fusion device. The following results will be recorded for each core: (1) the reason of biopsy (random biopsy; DSS tool alone; radiologist alone) (2) location (sextant and zone), and (2) histology result. Research cores will be evaluated by expert genitourinary pathologist, [name], and results will be communicated to the urologist.

Studies will be carried out using FDA approved 3 Tesla Philips, GE and Siemens MRI units at the University of Chicago Medical Center. All of the research MR sequences will be in compliance with FDA safety requirements and MR contrast agents will not be injected for research purposes.

C.2. MRI Data acquisition methods:

The data acquisition will consist of obtaining the standard clinical protocol and research sequences, in compliance with FDA safety requirements. Research sequences may include, but will not be limited to (1) KT-T2 sequence (high spatial resolution axial ME-TSE for T₂ measurements and anatomy visualization), and (2) axial HM-MRI with 4 b-values and 4 TEs for diffusion and T2 measurements. MR images will be acquired using Philips, GE or Siemens 3T clinical MR systems with a phased array surface receiver coil.

C.3. Study Endpoints and Statistical Analysis

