The major goal of this study is to compare the accuracy of the Risk Map DSS tool against the clinical accuracy of experienced radiologists in the context of the reference standard of biopsy histology. The primary endpoints will be ROC curve, AUC value, the secondary endpoint will be sensitivity, specificity, PPV, and NPV, and the tertiary endpoint will be correlation strength between the DSS tool output and tumor-specific Gleason scores. Both per-patient and per-tumor analyses will be conducted. For the per-patient analysis, patients who are diagnosed with PCa from the biopsy procedure will be considered as positive for PCa, and patients who are not diagnosed with PCa from the biopsy procedure will be considered as negative for PCa. For the per-tumor analysis, each individual PCa tumor diagnosed from the biopsy procedure will be analyzed separately, and biopsy sites that do not yield PCa diagnosis will be considered as negative for PCa. To ascertain a true positive biopsy, the finding and the biopsy must match in sextant and zone. If ambiguity in biopsy site arises with regard to indications from the DSS tool, or the radiologist's opinion, and the biopsy, expert radiologist ([name]) and pathologist ([name]) will review each case to make the determination. This will allow us to calculate the performance of: (1) the Risk Map DSS tool, (2) the radiologist, and (2) the standard sextant biopsy. We will evaluate these performance endpoints on clinically significant PCa (but we will have data for all tumors). Spearman correlation coefficient will be estimated in the usual manner.

C.4. Statistical power consideration

We expect the following level of performance: AUC 0.90±0.03, sensitivity 90±5%, specificity 90±4%, and statistically significant (Spearman's) correlation strength of 0.8 with tumor-specific Gleason scores. Variances are estimated based on the expectation of PCa diagnosis in 35% of 125 patients, and based on an empirical rule-of-thumb formula

for AUC and binomial probability for sensitivity and specificity. The estimated 95% confidence intervals (CIs) are: for AUC [0.87, 0.93], for sensitivity [0.85, 0.95], and for specificity [0.86, 0.94]. These uncertainty estimates do not include analysis of biopsy by sextant and zone of the 12-20 cores per patient; estimates of 12 by-location-analyses per patient reduce all uncertainties to about 1%. These estimates suggest that this protocol will produce meaningful performance estimates.

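### DSS targets the radiologist declines are not a recorded item and have no prescribed scoring, so per-tumor DSS PPV may rest on a selected or differently verified subset of calls

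*Combined protocol and SAP*

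**What the plan says.** Section B states that up to two DSS-determined targets are biopsied in addition to the systematic cores and the radiologist's targets, and makes the histology of all cores the reference standard. Section C.1 describes a single-arm study without blinding. It gives every patient a 12-core sextant biopsy and adds up to two DSS targets "if different from the already selected targets by the radiologist per standard of care". It then qualifies this: "Ultimately, the clinical radiologist will make the final decision on the targets to be biopsied".

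Data are recorded per core. The first item on the core record is "1) the reason of biopsy (random biopsy; DSS tool alone; radiologist alone", followed by location and histology. No item is listed for a DSS target that was proposed and not sampled.

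Section C.3 sets the comparison of the DSS with experienced radiologists as the main goal. ROC curve and AUC are primary, and "the secondary endpoint will be sensitivity, specificity, PPV, and NPV". For the per-tumor analysis, "biopsy sites that do not yield PCa diagnosis will be considered as negative for PCa", and for a true positive "the finding and the biopsy must match in sextant and zone". Where the biopsy site is ambiguous, an expert radiologist and a pathologist "will review each case to make the determination". Masking to the source of the call is not mentioned.

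**The concern.** In a comparison of two readers, neither should control whether the other's positive calls are verified. Here the radiologist's side can decline a DSS target, and no matching limit applies to the radiologist's own targets. If the radiologist tends to decline targets that look benign, the DSS calls that remain are enriched for cancer and apparent DSS PPV is too high. If declined targets are cancers that the radiologist does not recognise, the DSS loses credit for exactly the cases where it adds something.

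The core form would not show which of these happened, because a declined target has no core of its own. The three reason codes also cannot represent a target marked by both methods, although C.1 foresees overlap. This second gap is lesser: C.3 credits hits by location and not by code, so it affects accuracy only if DSS marks are not stored separately.

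**Working it through.** The plan states no figure on this point, so there is nothing to reproduce. The check has two parts.

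**1. What happens to a declined DSS target under the text**

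- *No core in its sextant and zone.* It is not a biopsied site, so it is neither a true positive nor a per-tumor negative. It drops out.
- *A core lies in the same sextant and zone.* Section B (all cores are the reference) and C.3 (match by sextant and zone) permit scoring from that core, but nothing prescribes it. The core was not aimed at the target, so it may miss a cancer there.
- *Ambiguous site.* C.3's review covers doubt about where a core lies, not the absence of a core.

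**2. Illustration of size**

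Only the ceiling comes from the documents: 125 patients x up to 2 targets = 250 DSS marks. All other inputs are assumptions:

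- h = 0.5, share of DSS targets also chosen by the radiologist (all sampled), with PPV q = 0.40
- p = 0.40, PPV of DSS-only targets that are biopsied
- v = 0.1, 0.3 or 0.5, share of DSS-only targets declined
- c = 0.10 or 0.70, cancer rate in declined targets
- s = 0.5, share of declined targets verified without error by a core in the same sextant and zone

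At the ceiling, 250 x 0.5 = 125 marks are DSS-only, and 12.5 to 62.5 of them are declined.

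True PPV = hq + (1-h)[p(1-v) + cv]

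Apparent PPV = {hq + (1-h)[p(1-v) + cvs]} / {h + (1-h)(1-v+vs)}

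Worked case, v = 0.5 and c = 0.10: true = 0.20 + 0.5(0.20 + 0.05) = 0.325; apparent = (0.20 + 0.5 x 0.225)/(0.5 + 0.5 x 0.75) = 0.3125/0.875 = 0.357; bias = +3.2 points.

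| v | bias, c = 0.10 | bias, c = 0.40 | bias, c = 0.70 |
|---|---|---|---|
| 0.1 | +0.7 | 0 | -0.7 |
| 0.3 | +2.1 | 0 | -2.1 |
| 0.5 | +3.2 | 0 | -3.2 |

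With s = 0 the same cells are ±1.5, ±4.5 and ±7.5 points. With q = 0.60 and s = 0.5 they are +1.0, +2.9 and +4.6 (c = 0.10), and -0.5, -1.3 and -1.8 (c = 0.70).

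*Differential verification.* Suppose instead that every declined target is scored by an unaimed core with assumed sensitivity 0.5 and no false positives, at v = 0.3.

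- c = 0.70: true 0.20 + 0.5(0.28 + 0.21) = 0.445; scored 0.20 + 0.5(0.28 + 0.105) = 0.3925, an error of -5.25 points. Dropping the declined targets gives 0.34/0.85 = 0.40, an error of -4.5.
- c = 0.10: true 0.355; scored 0.3475, an error of -0.75 points. Dropping gives 0.40, an error of +4.5.

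Neither rule is uniformly better, so the bounds must cover declined targets with negative unaimed cores as well as unsampled ones. Their width cannot exceed (1-h)v, that is 5, 15 or 25 points for the three values of v.

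*Site-level AUC.* A simulation used 125 patients x 12 locations, 44 patients with cancer (35%, from C.4), site AUC 0.90, the top two locations marked, and h and v as above. At s = 0.5, AUC shifted by less than 0.2 points when targets were declined at random, and by -1.4 to +0.6 points at the extremes (all declined cancer, all declined benign). At s = 0 the extremes were -3.7 to +1.2. The simulation treats all other locations as sampled, so it is indicative only.

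**The case against.** The strongest reply is that the 12-core biopsy gives every patient a reference standard, and that sections B and C.3 together already allow a declined target to be scored from any core in its sextant and zone. C.4 looks ahead to analysis by location: "These uncertainty estimates do not include analysis of biopsy by sextant and zone of the 12-20 cores per patient". This stands in part. A reader might infer that the plan has no means at all of verifying declined targets; the text does not support that. What is missing is a requirement to log them, a stated choice of scoring, and any default where no core matches. The text does not say that every zone of every sextant is cored, and an unaimed core is weaker evidence than a targeted one. The per-patient analysis is less exposed.

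A reader might also infer that the same individual is both comparator and gatekeeper. C.1 and C.3 speak of an expert, a clinical and experienced radiologists without identifying them with each other. The shared role is a reasonable inference and no more. Selective verification would arise whoever declined.

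Finally, no document gives a decline rate, and section B's default is that DSS targets are sampled. The rate may be low. This is correct, and it is why the figures above show a possible range and not an expected bias.

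**Conclusion.** The point holds as a cheap, worthwhile improvement, not as a flaw that invalidates the study. As written, declined DSS targets are not a recorded item, and per-tumor DSS PPV may rest on a selected or differently verified subset of DSS calls. Under the base assumptions the bias in PPV over all DSS targets is about 0.7 to 3.2 points in either direction. Its real size and sign cannot be known from the documents. The primary AUC is little affected in the half-verified illustration.

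Two stronger readings are tempting. One is to quote the bias for DSS-only targets, which is larger because shared targets do not dilute it. C.3 names PPV for the DSS tool as a whole and defines no DSS-only PPV. The other is that location-level specificity would be inflated by more than the roughly 1% uncertainty claimed in C.4. That needs systematic cores to reach every unmarked location yet miss declined ones. If partial coverage is applied to all non-targeted locations alike, the shift changes sign, and core coverage drives it instead of the radiologist's decision. The documents support neither reading.

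**What to change.** - Save the DSS and radiologist target lists, by sextant and zone, before biopsy.
- Replace the single reason code with three yes/no flags per core: systematic, DSS-marked, radiologist-marked.
- Log every declined DSS target and keep it in the per-tumor analysis, scored by any core in the same sextant and zone.
- Give best/worst-case bounds over all declined targets, both those unsampled and those negative only on unaimed systematic cores. Report the biopsied-targets-only result alongside.
- Mask the source of the call (DSS or radiologist) when ambiguous matches are adjudicated.
- Reconcile section B's unqualified statement that DSS targets are sampled with C.1's final-decision sentence, without changing who decides.

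The cost is a few form fields, two saved lists and a short paragraph in C.3. No extra biopsies or readers are needed. The downside is slightly more data capture and wider stated uncertainty for per-tumor PPV. The lists must be saved prospectively, since they may be hard to rebuild later without hindsight.

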We will test an artificial intelligence-based Risk Map DSS tool we have developed, which is based on and expanded from previously identified key MR image features that are effective for identifying PCa from normal prostate tissue, and which also correlates moderately with Gleason scores (ADC, T2, and tissue composition maps). The DSS tool will assist radiologists interrogate suspicious areas in the prostate that are potentially clinically significant PCa foci, and will identify up to two potential clinically significant tumor sites. In addition to systematic biopsies and the targets identified by the radiologist, up to two targets determined by the DSS tool will be biopsied. Biopsy histology results of all cores will be used as the reference standard to evaluate the performance of the Risk Map DSS tool.

C. METHODOLOGY

C.1. Study Design:

This is a prospective, single-arm, unblinded study of patients with known or suspected prostate cancer. A total of 125 patients will be enrolled.

Recruitment: We will recruit patients with known or suspected prostate cancer who have been referred to the Department of Radiology at the University of Chicago Medical Center for a diagnostic MRI exam of the prostate, to be followed by an MRI-guided fusion biopsy of the prostate, per standard clinical protocol.

All patients will be scanned using a standard clinical prostate MRI protocol. Research sequences will be added to the routine clinical exam. The research sequences will not exceed 15 minutes. The patients will not receive intravenous contrast agent as part of the research protocol.

All patients will then undergo a 12-core TRUS-guided or transperineal US-guided sextant random biopsy by their urologist at the Urology Clinic as their standard of care treatment. Additional biopsy targets may be selected based on an expert radiologist's interpretation of the patient's clinical MRI, as part of the clinical, standard of care MR targeted biopsy procedure. Up to two additional biopsy targets per patient will be selected by the Risk

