D. DURATION OF THE PROTOCOL

The probable duration of the study will be 3 years with review, at least annually, to recruit the target number of patients and complete all data analysis.

E. LOCATION WHERE RESEARCH WILL BE CONDUCTED

The study will be conducted on the FDA approved 3 Tesla Philips, GE or Siemens MRI scanners at the University of Chicago Medical Center, [name].

F. SAFETY MONITORING

We do not anticipate any adverse events. However, adverse events related directly to the study will be reported to the Cancer Center Clinical trials office following standard operating procedures outlined in the Cancer Center data safety and monitoring plan.

G. DESCRIPTION OF EXPERIMENTAL CONTROLS AND USE OF PLACEBOS

N.A.

H. TYPE AND NUMBER OF EXPERIMENTAL SUBJECTS

We will recruit 125 patients who will receive a diagnostic MRI exam of the prostate, to be followed by an MRI-guided fusion biopsy of the prostate.

Inclusion Criteria

We will recruit patients with known or suspected prostate cancer who have been referred to the Department of Radiology at the University of Chicago Medical Center for a diagnostic MRI exam of the prostate, to be followed by an MRI-guided fusion biopsy of the prostate. Written informed consent will be signed by the patients before the MRI examination.

Exclusion Criteria

Subjects will be screened and excluded per standard clinical protocol.

Also excluded are:

- Subjects incapable of giving informed written consent;

- Subjects who cannot adhere to the experimental protocols for any reason, or have an inability to communicate with the researcher;
- Subjects with psychiatric disorders that affect their ability to consent for themselves will be excluded and not the entire population of patients with psychiatric disorders.
- Prisoners;
- Minor children (under the age of 18 years old).
- Previous treatments (surgery, radiation, focal ablation, hormone or other chemotherapy) for prostate cancer.

Data to be collected

Demographic information will be collected from each recruited subject. The research team will also collect clinic visit, laboratory, imaging and pathology results relevant to the clinical question for each subject.

J. SHARING RESEARCH RESULTS:

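### Per-patient disease status comes from the study biopsy alone, so an eligible man with previously proven clinically significant cancer counts as negative if the study cores miss it

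*Combined protocol and SAP*

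**What the plan says.** Section C.1 describes a single-arm, "unblinded study of patients with known or suspected prostate cancer", with 125 patients. The inclusion criteria in section H repeat the population: "We will recruit patients with known or suspected prostate cancer who have been referred to the Department of Radiology". Prior cancer leads to exclusion only if it was treated; the listed criterion is "Previous treatments (surgery, radiation, focal ablation, hormone or other chemotherapy) for prostate cancer". Untreated known cancer therefore stays eligible.

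Section B names the reference standard: "Biopsy histology results of all cores will be used as the reference standard to evaluate the performance of the Risk Map DSS tool". Section C.3 turns this into two rules. Per patient, "patients who are not diagnosed with PCa from the biopsy procedure will be considered as negative for PCa". Per tumor, "biopsy sites that do not yield PCa diagnosis will be considered as negative for PCa". Neither rule has an exception for a man diagnosed before enrolment.

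Three other statements matter. Section C.3 says the endpoints are evaluated on clinically significant cancer, although data on all tumors will be held. The background section, just before A.1, defines this as Gleason above 6, or Gleason 6 or less if not localized. Expert review in C.3 is reserved for doubt about the biopsy site. Section H collects relevant pathology results, but no section gives them a role in disease status.

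**The concern.** Any biopsy reference standard misses some cancers. Here the point is narrower: for some men, contrary histology already exists at enrolment and the stated rule sets it aside. The main goal in C.3 is to compare the DSS tool with experienced radiologists, with ROC curve and AUC as primary endpoints and sensitivity, specificity, PPV and NPV as secondary.

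For a man with proven significant cancer that the study cores miss, the scoring goes wrong in three ways. A patient-level flag counts against the tool that raised it. A failure to flag is credited. The man also disappears from the group in which sensitivity is measured. If the two readers flag different men of this kind, the comparison between them is distorted as well. Section C.3 also evaluates the standard sextant biopsy, which in these men is credited with a true negative for the miss itself.

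**Working it through.** **1. The plan's own figures.** Section C.4 expects a cancer diagnosis in 35% of 125 patients: 0.35 × 125 = 43.75 positives and 81.25 negatives, taken below as 44 and 81. Expected specificity is 0.90, with a stated interval of 0.86 to 0.94. The binomial standard error is √(0.90 × 0.10 / 81.25) = 0.033, so the stated ±0.04 is about one standard error rounded up. A 95% half-width would be 1.96 × 0.033 = 0.065, giving a lower limit of 0.835. That mismatch is a separate matter. Here 0.86 serves only as the plan's own yardstick.

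**2. Inputs the documents do not give.** These are the share of men with known cancer, the share of those whose prior cancer was clinically significant, the chance that all study cores miss it, and how often such men are flagged. The number mislabelled, m, and their flag rate, f, are therefore assumptions.

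**3. Specificity.** With m mislabelled men among 81 recorded negatives and a true specificity of 0.90:

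recorded specificity = [0.90 × (81 − m) + (1 − f) × m] / 81

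| m | f | Calculation | Recorded specificity |
|---|---|---|---|
| 4 | 90% | (69.3 + 0.4) / 81 | 0.8605 |
| 5 | 90% | (68.4 + 0.5) / 81 | 0.851 |
| 8 | 50% | (65.7 + 4.0) / 81 | 0.8605 |
| 9 | 50% | (64.8 + 4.5) / 81 | 0.856 |
| 9 | 10% | (64.8 + 8.1) / 81 | 0.900 |
| 9 | 0% | (64.8 + 9.0) / 81 | 0.911 |

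The smallest numbers that fall below 0.86 are 5 men at 90% and 9 men at 50%. Against 0.835 they would be 7 men (0.90 − 0.8 × 7/81 = 0.831) and 14 men (0.90 − 0.4 × 14/81 = 0.831). At f = 10% there is no bias, and below that specificity is flattered.

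**4. Sensitivity.** Suppose 90% of the 44 biopsy-positive men are flagged: 0.90 × 44 = 39.6. Restoring 9 missed men flagged at 50% gives (39.6 + 4.5) / 53 = 0.83, while the rule reports 0.90. Restoring 5 men flagged at 90% gives (39.6 + 4.5) / 49 = 0.90, so nothing changes. Sensitivity is flattered only if the missed men are flagged less often than the detected ones.

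**5. AUC.** If missed cancers score like detected ones, recorded AUC = (1 − m/81) × 0.90 + (m/81) × 0.50. For m = 5 this is 0.875 against a true 0.90.

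**6. Comparison of the two readers.** Each mislabelled man flagged by one reader and not the other shifts the difference in specificity by 1/81, or 1.2 percentage points, against the one that flagged him.

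**The case against.** The strongest reply is that few men may be affected. The endpoints target clinically significant cancer, so known localized Gleason 6 with a negative study biopsy is classified correctly. What remains is known significant cancer, untreated, missed by 12 systematic cores plus any targeted cores. A flag also prompts sampling: radiologist targets and up to two DSS targets are biopsied, subject to the radiologist's final decision. Men whose cores are all negative may therefore be enriched for men nobody flagged, and the bias on specificity could be small or even upward. All of this stands, and it is why no size can be claimed.

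Four stronger readings are tempting, and the documents do not support them:

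- **A range for the lost specificity.** A reader might assume a known share and a miss rate and compute one. Neither has a source, and plausible-looking pairs conflict with C.4. At 40% known and 10% missed, known men alone give 125 × 0.40 × 0.90 = 45 positives, more than the 43.75 expected in total.
- **All flags in these men are correct.** A prior diagnosis does not validate a flag at a sampled benign site. C.3 requires a match in sextant and zone for a true positive biopsy. The point is confined to patient-level status.
- **The rule always lowers accuracy.** The direction depends on the flag rate, as shown in the working.
- **Prior pathology should become the primary reference.** That would give known men two chances to be positive and suspected men one. The study is unblinded, and nothing withholds the earlier result from the clinical radiologist, so it could favour the radiologist in the main comparison.

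**Conclusion.** The concern holds in limited form. Eligibility and the per-patient rule together can label a man with previously proven, untreated, clinically significant cancer as disease-negative, and no provision in the plan catches this. It is a stated rule with a wrong result for a definable group.

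The number of such men cannot be derived. The thresholds of 5 men at a 90% flag rate or 9 at 50% are illustrations. They assume a true specificity of 0.90 and about 81 recorded negatives. Section C.4 does not say whether its 35% means any cancer or significant cancer; if any, there would be more than 81 negatives for the significant-cancer target and each mislabelled man would weigh less.

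The matter is worth settling before analysis because the remedy is cheap and an unblinded study is poorly placed to relabel men afterwards. It does not call the design into question.

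**What to change.** At enrolment, record whether cancer is known or suspected and, if known, the prior biopsy grade and whether disease was localized, so that the plan's own definition of significance can be applied. Keep the study biopsy as the primary reference standard, and pre-specify in C.3:

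1. Per-patient results reported separately for known and suspected men.
2. A per-patient sensitivity analysis in which men with prior clinically significant cancer and a negative study biopsy are not counted as negatives. Run it once with them excluded and once with each man classified by the highest grade in prior or study pathology. In the 5-man illustration, exclusion returns specificity to 68.4 / 76 = 0.90.

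State the number of such men with the results, and state that the highest-grade version is supportive only, because it verifies known and suspected men differently and may favour a radiologist who knows the earlier result.

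The cost is a few data fields and a paragraph of text. Section H already collects relevant pathology, and no procedure or sample size changes. The price is smaller subgroups with wider intervals. The change does not address cancers missed in suspected men or the per-tumor analysis.

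### The per-tumor analysis sets tumors against an undefined biopsy site, and C.4 states its precision for a third unit, so PPV and NPV depend on how many negative sites are sampled per tumor

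*Combined protocol and SAP*

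**What the plan says.** C.3 makes accuracy the main outcome: "The primary endpoints will be ROC curve, AUC value, the secondary endpoint will be sensitivity, specificity, PPV, and NPV". It adds that "Both per-patient and per-tumor analyses will be conducted", and names neither level as principal. In the per-tumor analysis, "each individual PCa tumor diagnosed from the biopsy procedure will be analyzed separately, and biopsy sites that do not yield PCa diagnosis" are the negatives. The term biopsy site is not defined. No rule says how several positive cores merge into one tumor, or how several negative cores at one place are counted. The sextant-and-zone match in C.3 is given as a condition for a true positive only. The expert review of ambiguous cases settles which biopsy belongs to which finding, not what is counted.

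The number of cores varies. C.1 says: "All patients will then undergo a 12-core TRUS-guided or transperineal US-guided sextant random biopsy". It continues: "Additional biopsy targets may be selected based on an expert radiologist's interpretation of the patient's clinical MRI". Then: "Up to two additional biopsy targets per patient will be selected by the Risk" Map DSS tool. Cores per target are not fixed.

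C.4 gives per-patient margins and then says: "These uncertainty estimates do not include analysis of biopsy by sextant and zone of the 12-20 cores per patient". It goes on: "estimates of 12 by-location-analyses per patient reduce all uncertainties to about 1" percent.

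**The concern.** Three counting units are in play: tumors for positives, sites for negatives, and 12 locations per patient for precision. A tumor hit by three cores is one positive. Three negative cores in one place are one negative or three, depending on what site means.

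PPV and NPV depend on the ratio of positives to negatives, so they follow the biopsy scheme as well as the tool. If a site is a core, there is a second effect. Cores beyond the 12 systematic ones go mainly to flagged places, so the mix of negatives changes, and specificity and AUC can change with it.

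The stated goal is to compare the DSS tool with radiologists, and the study is unblinded. A unit that is settled only once results are visible would allow the same data to give materially different accuracy figures. The about 1% in C.4 would also promise a precision that the C.3 unit cannot deliver.

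**Working it through.** **Inputs from the documents.** 125 patients, 35% with PCa (43.75 positive, 81.25 negative), sensitivity and specificity 90%, AUC 0.90, 12 locations and 12 to 20 cores per patient (C.1, C.4).

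**Assumed, not in the documents.** 1 to 2 tumors per positive patient (44 to 88 tumors), two positive cores per tumor, and 1, 2 or 4 cores per false target.

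**1. Reproducing C.4.** For a proportion, SE = √(p(1−p)/n); for AUC, the Hanley-McNeil formula.
- Per patient: sensitivity √(0.09/43.75) = 4.5%, specificity √(0.09/81.25) = 3.3%, AUC 0.033. C.4 states 5%, 4% and 0.03, so its margins correspond roughly to one standard error.
- By location: 12 × 125 = 1,500, of which 35% is 525 positive and 975 negative. Sensitivity √(0.09/525) = 1.3%, specificity √(0.09/975) = 1.0%, AUC 0.009.

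So about 1% reproduces as one standard error, with independent locations and 35% of locations positive. Since 525/43.75 = 12, this amounts to every location being positive in every patient with cancer.

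**2. The same precision with C.3's positives.** With 44 tumors, √(0.09/44) = 4.5%; with 88, √(0.09/88) = 3.2%. The about 1% for sensitivity does not carry over.

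**3. PPV and NPV as the number of sites changes.** Take site as core, 44 tumors, and sensitivity and specificity fixed at 90%. True positives are 0.9 × 44 = 39.6 and false negatives 4.4.
- 12 cores: negatives 1,500 − 88 = 1,412. PPV = 39.6/(39.6 + 141.2) = 21.9%; NPV = 1,270.8/(1,270.8 + 4.4) = 99.65%.
- 20 cores: negatives 2,500 − 88 = 2,412. PPV = 39.6/(39.6 + 241.2) = 14.1%; NPV = 2,170.8/(2,170.8 + 4.4) = 99.80%.

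With 88 tumors, PPV falls from 37.4% to 25.4%. Specificity and AUC do not move here.

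**4. Specificity when extra cores repeat a flagged place.** Take site as core and a cancer-free patient with 12 negative systematic cores, none of them in the flagged location, and one false target given c cores. Specificity = 12/(12 + c):
- c = 1: 12/13 = 92.3%
- c = 2: 12/14 = 85.7%
- c = 4: 12/16 = 75.0%

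Across the cohort, with one false target per patient, 1,412/(1,412 + 125c) gives 91.9%, 85.0% and 73.8%. If a site is a target, the one-patient figure stays at 12/13 = 92.3% for any c. On a fully sampled 12-location grid it is 11/12 = 91.7% for any c.

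**5. The direction is not fixed.** Suppose instead that the tool makes two false calls per patient (250 in all) and the added cores are benign and unflagged. Specificity then rises from 1 − 250/1,412 = 82.3% at 12 cores to 1 − 250/2,412 = 89.6% at 20.

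**6. AUC, illustration only.** Suppose AUC is 0.90 against systematic benign sites and targeted benign sites score 0.5 to 1 SD higher. AUC against the targeted sites alone is then 0.823 to 0.717. Weighting 12 systematic and 2 targeted negatives gives 0.89 to 0.87; 12 and 8 gives 0.87 to 0.83.

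**The case against.** The strongest reply is that the documents do not say a site is a core. Section B speaks of tumor sites for the places the tool identifies and of cores separately. C.1 records sextant and zone for each core, C.3 matches on them, and C.4 refers to analysis by sextant and zone. A location reading is at least as natural, and under it the figures in step 4 largely disappear. This stands. The defect is an undefined unit, not an established miscount. Even so, a tumor would still be set against a location, and C.3 and C.4 would still disagree.

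A reader might also infer more than the documents support:
- **That the tumor/site mismatch by itself distorts specificity and AUC.** It does not. Specificity uses negatives only, and AUC does not depend on the class ratio. Both move only if the mix of negatives changes.
- **That the step 4 values should be judged against C.4's 90±4% for specificity.** That is a per-patient figure; step 4 is a conditional illustration with assumed cores per target.
- **That the DSS tool or the radiologist is penalised in the comparison.** Nothing says that either receives more cores per target, and step 5 shows that extra cores can also raise specificity.

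**Conclusion.** The point holds as a gap in definition with a calculable consequence. The mixed unit makes PPV and NPV depend on the number of negative sites per tumor: PPV moves from 21.9% to 14.1% (44 tumors) or from 37.4% to 25.4% (88 tumors) between 12 and 20 cores. This rests on the core reading, two positive cores per tumor and accuracy fixed at 90%. Effects on specificity and AUC are possible under the core reading only, and their size and direction depend on where the extra cores go.

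The conflict between C.3 and C.4 does not depend on what site means, because positives in C.3 are tumors: a standard error of sensitivity of 4.5% to 3.2% (44 to 88 tumors, assumed) against about 1%. The per-patient analysis is free of this problem, so the matter is worth correcting but does not undermine the whole plan.

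**What to change.** In C.3, make the sampled sextant-by-zone location the single unit for positives and negatives:
- Count each location once, as positive if any core in it shows clinically significant PCa.
- Score it by the maximum DSS risk, or by the radiologist's category, in that location.
- Leave locations without a core out of the accuracy denominators and report how many there are. C.1 does not say that both zones of every sextant are cored.
- Compute intervals by resampling patients.

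In C.4, restate the about 1% for this unit, with clustering and a realistic share of positive locations. As a guide, with all 1,500 locations sampled, an assumed 88 to 132 positive and 90% accuracy, PPV is about 36% to 46% and NPV about 99.3% to 98.9%. The standard error of sensitivity is √(0.09/88) = 3.2% to √(0.09/132) = 2.6% before any allowance for clustering. Repeated cores in one location no longer change the denominators, although more cores can still change which locations are sampled or found positive.

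The cost is wording: C.1 already records location and histology for every core. The drawbacks are that two tumors in one location count as one, a tumor spanning several locations counts more than once, and the stated precision becomes less favourable.
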